10.4. Unexpected Adverse Reactions

An AE is “unexpected” if its nature and severity are not consistent with the information about the study drug provided in the Reference Safety Information in the IB.

10.5. Recording Adverse Events

10.5.1. General

All AEs will be recorded from the time the study participant signs the ICF form until the EOS Visit or ET Visit, whichever comes first. All AEs must be reported on the AE electronic case report form (eCRF) via the electronic data capture system. The Investigator is responsible for evaluating all AEs, obtaining supporting documents, and ensuring that documentation of the event is complete. Details of each reported AE must include at a minimum severity, relationship to study treatment, duration, and outcome. All serious and nonserious AEs must be followed until they are resolved or stabilized, or until reasonable attempts to determine resolution of the event are exhausted.

Any participant who experiences an AE may be discontinued from study treatment at any time at the discretion of the Investigator. The Sponsor/Medical Monitor(s) must be notified of the study participant discontinuation.

10.5.2. Diagnosis Versus Signs and Symptoms

If known, a diagnosis should be recorded in the eCRF rather than individual signs and symptoms (eg, record only liver failure or hepatitis rather than jaundice, asterixis, and elevated transaminases). However, if a constellation of signs and/or symptoms cannot be medically characterized as a single diagnosis or syndrome at the time of reporting, each individual event should be recorded separately in the eCRF. If a diagnosis is subsequently established, it should be reported as follow-up information.

10.5.3. Abnormal Laboratory Values

Clinically significant laboratory abnormalities will be recorded in the AE eCRF (eg, abnormalities that have clinical sequelae, more frequent follow-up assessments, or further diagnostic investigation). If the clinically significant laboratory abnormality is a sign of a disease or syndrome (eg, alkaline phosphatase and bilirubin 5 × ULN associated with cholecystitis), only the diagnosis (eg, cholecystitis) should be recorded in the eCRF.

If the clinically significant laboratory abnormality is not a sign of a disease or syndrome, the abnormality itself should be recorded on the eCRF. If the laboratory abnormality can be characterized by a precise clinical term, the clinical term should be recorded. For example, a serum potassium level of 7.0 mEq/L should be recorded as “hyperkalemia”.

Observations of the same clinically significant laboratory abnormality from visit to visit should not be repeatedly recorded on the AE eCRF, unless their severity, seriousness, or etiology changes.

10.6. Reporting Adverse Events

10.6.1. Serious Adverse Events

All SAEs, regardless of causal attribution, must be reported by the Investigator or designee or site personnel within 24 hours of awareness by completing the paper SAE report forms and submit via fax or email to Sponsor's Pharmacovigilance or designated CRO.

The Sponsor or designee may request additional source documentation pertaining to the SAE from the investigational site. Follow-up reports must be submitted within 24 hours of awareness, and participant identifier information (eg, name, medical record number) must be redacted in the hospital discharge summaries, autopsy reports, and/or death certificates.

Follow-up SAE information must be submitted within 24 hours of awareness as additional information becomes available. All SAEs regardless of causal attribution must be followed to resolution or stabilization, or until reasonable attempts to determine resolution of the SAE are performed.

Investigators are not obligated to actively seek SAE information from participants that complete the study, but investigators are encouraged to notify the Sponsor, or designee, of any SAEs of which they become aware occurring at any time after a participant has discontinued or completed the study that they judge may be reasonably related to treatment with study drug or study participation.

10.6.2. Reporting Suspected Unexpected Serious Adverse Reactions and Urgent Safety Issues

The Sponsor or designee is responsible for reporting suspected unexpected serious adverse reactions (SUSARs) to regulatory agencies, competent authorities, IRB, and Investigators as per local laws and regulations. Fatal and life-threatening SUSARs will be submitted no later than 7 calendar days of the Sponsor's or designee's first knowledge of the event and follow-up information submitted within an additional 8 calendar days, or as otherwise required per local laws and regulations. All other SUSARs will be submitted within 15 calendar days of the Sponsor's or designee's first knowledge of the event. The Investigator is responsible for notifying the local IRB of all SAEs that occur at his or her site as required by local regulations or IRB policies, if this responsibility resides with the site.

Investigators are required to report any urgent safety matters to the Sponsor or designee within 24 hours of awareness. The Sponsor or designee will inform regulatory authorities, IRBs, and Investigators, as applicable, of any events (eg, change to the safety profile of GBT021601, major safety findings that may place study participants at risk) that may occur during the clinical study that do not fall within the definition of a SUSAR but may adversely affect the safety of study participants.

10.7. Pregnancy

If a participant becomes pregnant while on study, the pregnancy must be reported to the Sponsor or designee within 24 hours of awareness. The Investigator will discuss the risks and concerns of study drug exposure to a developing fetus and counsel the participant and/or pregnant partner (or ensure such counseling is provided).

Reported pregnancy of a participant while participating in this study will be monitored for the full duration of the pregnancy, and/or followed through a definitive outcome (ie, birth or spontaneous or elective abortion). Pregnancies in partners of male study participants will similarly be monitored for the full duration of the pregnancy and/or followed through a definitive outcome (ie, birth or spontaneous or elective abortion).

An uncomplicated pregnancy will not be considered an AE or SAE. Pregnancy complications such as spontaneous abortion/miscarriage and congenital anomalies are considered SAEs and must be reported as described in Section 10.6.1. Note that an elective abortion is not considered an SAE. Pregnancy and pregnancy outcomes must be reported on a Pregnancy Notification Form or Pregnancy Outcome Form, respectively, and sent to the Sponsor or designee within 24 hours of the Investigator site personnel learning of the pregnancy or pregnancy outcome.

The child born to a female participant or partner of a male participant exposed to study drug will be followed for 3 months after delivery. The outcome of any pregnancy and the presence or absence of any congenital abnormality will be recorded in the Pregnancy Outcome Form and reported to the Sponsor or designee. Any congenital abnormalities in the offspring will be reported as an SAE and must be reported as described in Section 10.6.1.

Information regarding pregnancy testing (including definition of females of childbearing potential) is provided in Section 6.5.3. Highly effective means of contraception are listed in Section 6.5.3.3.

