Adverse events	X	X	X	X	X	X	X	X	X	X	X

Abbreviations: aPTT, activated partial thromboplastin time; CoV, coronavirus; ECG, electrocardiogram; eGFR, estimated glomerular filtration rate; EOS, end of study; ET, early termination; FSH, follicle-stimulating hormone; HIV, human immunodeficiency virus; INR, International Normalized Ratio; PCR, polymerase chain reaction; PT, prothrombin time; RBC, red blood cell; SARs, severe acute respiratory syndrome; SCD, sickle cell disease.

^a History update, if any, will be obtained.

^b A full physical examination should be conducted at Screening. All subsequent physical examinations should be signs and symptoms driven.

^c Vital Signs include blood pressure, heart rate, respiration rate, body temperature while the participant is in a supine position. See [Table 2](#).

^d 12-Lead ECG on Day 1 should be performed within 30 minutes prior to dose, and 4 and 8 hours after dosing, then in the morning of each day of confinement and at any time at other clinic visits. See [Table 2](#).

^e The Lipid Panel is done at the Screening Visit only.

^f The eGFR will be calculated at Screening and confirmed on Day -1 using the Cockcroft-Gault formula.

^g A serum pregnancy test will be conducted at Screening and ET and urine pregnancy test at all other visits. A serum pregnancy test will also be conducted when a positive urinary pregnancy test occurs for confirmation.

^h RBC deformability and dense cells will be tested on Day 1 predose and 12 hours postdose.

Table 2: Schedule of Select Study Procedures (First 48 hours)

Procedure	Sampling Timepoint										
	Pre dose	Postdose (hours)									
		0.25 hr	0.5 hr	1 hr	2 hr	4 hr	6 hr	8 hr	12 hr	24 hr (Day 2)	36 hr
HR and BP ^{a, b}	X				X	X	X	X	X	X	X
RR and Body Temperature ^{a, b}	X									X	X
12-lead safety ECGs ^{b, c}	X			X		X		x		X	X
PK Sampling ^d	X	X	X	X	X	X	X	X	X	X	X

Abbreviations: BP, blood pressure; ECG, electrocardiogram; HR, heart rate; PK, pharmacokinetic; RR, respiratory rate; SAD, single ascending dose.

Note: For procedures scheduled to be performed at the same time, priority is to be given to collection of the PK samples at the designated time.

ECGs, followed by vital signs, are to be taken before PK sampling, unless PK samples will be late as a result. If times are delayed due to technical difficulties, this will be noted, but not considered a protocol deviation.

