^a HR, BP, RR, and body temperature will be measured after a participant has rested for at least 5 minutes in the supine position.

^b Window for collection: up to 3 hours predose, \pm 15 minutes up to 12 hours post, \pm 30 minutes if \geq 24 hours postdose.

^c ECGs (12-lead) will be collected in triplicate within 5 minutes after a participant has rested at least 5 minutes in the supine position. Pre-dose ECGs and vital signs on Day 1 may be performed within 3 hours prior to dosing.

^d Predose blood PK sample to be collected within 60 minutes prior to dosing. Postdose collection windows are: 0.25, 0.5 and 1 hour \pm 2 mins, 2 to 24 hours \pm 5 mins, 36 and 48 hours \pm 10 mins.

Table 3: Schedule of Assessments for Multiple Ascending-dose Period (Part B)

Study Week	Week 8 (Day 56 + 4 weeks) ^a	Week 9 (Day 63 ± 3 days)	Week 10 (Day 70 ± 3 days)	Week 11 (Day 77 + 3 days)	Week 12 (Day 84 ± 3 days)	Week 13 (Day 91 ± 3 days)	Week 14 (Day 98) ± 3 days	Week 15 (Day 105) ± 3 days	Week 16 (Day 112) EOT	Every 4 weeks through EOB ± 7 days	Day 218 (EOB/ET)
Physical examination	X					X			X		X
Height											
Weight	X		X								
Vital signs ^c	X	X	X	X	X	X	X	X	X		X
12-lead ECG (triple tracing) ^d	X					X			X		X
Study drug administration	X ^e	X	X	X	X	X ^f	X	X	X		
Dispense patient diary ^g	X	X	X	X	X	X	X	X			
Collect patient diary ^g		X	X	X	X	X	X	X	X		
Hematology and serum chemistry	X		X		X	X		X	X	X	X
Blood smear ^h	X								X		X
Serum erythropoietin	X					X	X		X		
eGFR ⁱ	X					X					X
Urinalysis	X					X					X
Pregnancy test (women only) ^j	X					X					
Pharmacokinetic assessment (whole blood and plasma) ^k	X	X	X	X	X	X	X	X	X	X	X

Study Week	Week 8 (Day 56 + 4 weeks) ^a	Week 9 (Day 63 ± 3 days)	Week 10 (Day 70 ± 3 days)	Week 11 (Day 77 + 3 days)	Week 12 (Day 84 ± 3 days)	Week 13 (Day 91 ± 3 days)	Week 14 (Day 98) ± 3 days	Week 15 (Day 105) ± 3 days	Week 16 (Day 112) EOT	Every 4 weeks through EOB ± 7 days	Day 218 (EOB/ET)
Hemoximetry ^k	X	X	X			X		X	X		X
RBC deformability, dense cells (if feasible) ^k	X	X	X			X		X	X		X
Concomitant medications	X	X	X	X	X	X	X		X		X
Adverse events	X	X	X	X	X	X	X		X		X
Clinic visit	X	X	X	X	X	X	X		X		X

Abbreviations: ECG, electrocardiogram; eGFR, estimated glomerular filtration rate; EOB, end of Part B; ET, early termination; RBC, red blood cell.

Note: For procedures scheduled to be performed at the same time, priority is to be given to collection of the PK samples at the designated time.

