5. SELECTION AND WITHDRAWAL OF PARTICIPANTS

5.1. Participant Inclusion Criteria

Participants must meet all inclusion criteria to be eligible for study participation.

1. Male or female with SCD.
2. Documentation of SCD genotype homozygous for sickle cell allele (HbSS) or double heterozygote for HbS and β-0 thalassemia (HbSB).
3. Age 18 to ≤ 60 years, inclusive.
4. Hb ≥ 5.5 and ≤ 10.5 g/dL during Screening and considered stable and close to Baseline by the Investigator.
5. For participants taking HU, the dose in mg/kg must be stable for at least 90 days prior to signing the informed consent form (ICF) and with no anticipated need for dose adjustments during the study in the opinion of the Investigator.
6. Female participants of child-bearing potential, must agree to use highly effective methods of contraception or practice abstinence from study start to 165 days after the last dose of study drug. Males who are not surgically sterile with partners of childbearing potential must agree to use a highly effective method of birth control during the study and for 165 days after the last dose of study drug. A highly effective method of contraception is defined as one that results in a low documented failure rate when used consistently and correctly such as: condom plus use of an intrauterine device; intrauterine system or hormonal method of contraception (oral, injected, implanted, or transdermal) for their female partner; or sexual abstinence. In addition, males who are not surgically sterile with a partner who is pregnant must agree to condom use or maintain sexual abstinence during the study and for 165 days after the last dose of study drug.
7. Males must agree to not donate sperm from study start through 165 days after the final dose.
8. Participant has provided documented informed consent.

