6.5.3.2. Instructions for Male Participants Capable of Fathering a Child

There is no information about effects that GBT021601 could have on male sperm and on the development of the fetus in humans. Therefore, it is important that the female partners of male participants do not become pregnant during the study and for a total period of 165 days after the male participant has taken the last dose of GBT021601.

As a precaution, all male participants who are sexually active and not surgically sterile should avoid fathering a child by either true abstinence or the use of barrier methods of contraception plus highly effective contraception for their female partner if of childbearing potential.

6.5.3.3. Acceptable Forms of Contraception for Male Participants with Female Partners Capable of Reproduction

Refer to Inclusion Criterion 6.

Male participants who are not surgically sterile with partners of childbearing potential must agree to use a highly effective method of birth control during the study and for 165 days after the last dose of study drug. A highly effective method of contraception is defined as one that results in a low documented failure rate when used consistently and correctly such as: condom plus use of an intrauterine device; intrauterine system or hormonal method of contraception (oral, injected, implanted, or transdermal) for their female partner; or sexual abstinence.

Male participants who are not surgically sterile with a partner who is pregnant must agree to condom use or maintain sexual abstinence during the study and for 165 days after the last dose of study drug.

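### The duty to report participant pregnancies is tied to being on study, which on the dated schedule ends 45 to about 109 days before the protocol's 165-day post-dose contraception period, and Part B schedules no pregnancy test after Day 91

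*Protocol*

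**What the plan says.** **Contraception period.** Protocol Section 5.1, criterion 6, binds women of childbearing potential "from study start to 165 days after the last dose of study drug". Section 6.5.3.2 asks that partners of male participants avoid pregnancy during the study and "for a total period of 165 days after the male participant has taken the last dose of GBT021601". Its stated reason is: "There is no information about effects that GBT021601 could have on male sperm and on the development of the fetus in humans".

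**Reporting.** Section 10.7 opens with "If a participant becomes pregnant while on study, the pregnancy must be reported to the Sponsor or designee within 24 hours of awareness". A later sentence, on monitoring a participant's pregnancy to outcome, is again limited to the time of participation. Three other provisions of the section have no such limit: monitoring of partner pregnancies, the notification and outcome forms (due 24 hours after site staff learn of a pregnancy or its outcome), and the three-month follow-up of exposed children. Section 4.6 says participation ends when all assessments and visits are complete.

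**Testing in Part B.** In Protocol Table 3 the row "Pregnancy test (women only) ^j" is marked at Week 8 (Day 56) and Week 13 (Day 91) only. SAP Table 3-3 marks the same two visits. Dosing runs through Week 16 (Day 112). Nothing is marked at Week 16, at the 4-weekly follow-up or at Day 218 (EOB/ET).

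**Testing elsewhere.** Table 1 footnote g says "A serum pregnancy test will be conducted at Screening and ET and urine pregnancy test at all other visits", but Table 1 has no ET column. In Part C, Table 4 and SAP Table 3-4 mark tests at Screening, Day 1, Week 6 (end of treatment), Week 14 and the Final Visit.

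**The concern.** The protocol asks participants to avoid pregnancy for 165 days after the last dose, but ties the site's duty to report a participant's pregnancy to a shorter and variable period. A woman who conceives after her last visit but inside the 165 days is in a period the protocol treats as one of possible fetal risk, and the first sentence of Section 10.7 does not reach her.

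The route through serious adverse events is weak. Under Section 10.6.1, investigators need not actively seek such events once a participant has completed the study, and are only encouraged to pass on related ones they hear of.

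In Part B there is also no scheduled test at or after the last dose to detect a pregnancy conceived under treatment. At stake is the capture of exposed pregnancies and their outcomes. In a study of about six participants and with no human fetal data, missing one could mean missing all such evidence from this trial.

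**Working it through.** The documents give no derivation for 165 days, so that figure is taken as stated. The rest is day counting on nominal visit days.

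**Inputs**
- Contraception period: 165 days after the last dose (Section 5.1; Section 6.5.3.2).
- Part B: last test Day 91, last dose Day 112, final visit Day 218 (Table 3). Follow-up is capped at 120 days after the last dose (Synopsis).
- Part C: Week 6 dose on Day 42, last dated visit Week 14 on Day 98 (Table 4). The Final Visit has no date.

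**The plan's own 218 days.** 56 + 42 + 120 = 218 matches the Synopsis maximum (8-week single-dose period, 6-week multiple-dose period, 120 days). Counted from the Day 112 dose in Table 3, the 120-day cap falls on Day 112 + 120 = 232. Both end points are used below.

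**Part B testing**
- Last test to last dose: 112 − 91 = 21 days.
- End of the 165 days: 112 + 165 = Day 277.
- Last test to that day, for someone who never enters Part C: 277 − 91 = 186 days without a scheduled test.

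**Part B reporting**
- To Day 218: 218 − 112 = 106 days on study, 106/165 = 64.2%. Remainder 165 − 106 = 59 days (35.8%).
- To the 120-day cap: 120/165 = 72.7%. Remainder 165 − 120 = 45 days (27.3%).

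**Part C reporting**
- End of the 165 days: 42 + 165 = Day 207.
- If follow-up ends at Week 14: 98 − 42 = 56 days on study, 56/165 = 33.9%. Remainder 165 − 56 = 109 days (66.1%).
- With the ±3-day visit windows: 95 − 45 = 50 to 101 − 39 = 62 days on study, leaving 103 to 115 days.
- If the 4-week and 8-week follow-ups were consecutive: 28 + 56 = 84 days on study, leaving 165 − 84 = 81 days (49.1%).

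**Which Part C end point?** The Synopsis gives a 4- and 8-week follow-up, and Section 4.5 gives 8 weeks only. Weeks 10 and 14 lie 4 and 8 weeks after Week 6, which favours the 56-day reading. The 53-week maximum does not settle it. Screening, Day 218, Part C screening and Day 98 give 28 + 218 + 28 + 98 = 372 days, or 53.1 weeks; but 31 + 4 + 6 + 4 + 8 = 53 weeks fits as well. The documents state neither breakdown.

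**A further inconsistency.** Section 3.4.2.3 describes 4 loading days plus 81 days of maintenance, against about 6 weeks elsewhere. On that reading the last dose is Day 85 and Week 14 falls 98 − 85 = 13 days later, unless visits are added as Table 4 footnote d allows.

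**The case against.** A reader might infer that most of the 165 days goes unmonitored. The documents do not support that as a general statement. In Part B, 64% to 73% of the period is on study, so the reporting duty covers most of it; only scheduled testing is absent throughout. In Part C there are tests at the end of treatment and in follow-up, and the 66% shortfall depends on follow-up stopping at Week 14, while the Final Visit has a test but no date.

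A reader might also infer that a late pregnancy cannot be reported, or that its follow-up never starts. That too goes beyond the text. The partner, form and exposed-child provisions of Section 10.7 are not limited to the time on study. What remains is an inconsistency within the section: two sentences restrict the duty for participants and others do not.

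Two practical objections have force. Section 3.3.2 says Part B dosing was complete, with follow-up ongoing, so a Week 16 test would no longer reach the six participants already dosed. Those who go on to Part C are tested again at its Screening and Day 1 visits, so the 186-day figure applies only to someone who stops after Part B. Part C entry depends on eligibility, so such participants can exist.

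Finally, no passage says testing must span the contraception period, and this point does not claim that it must. The testing inconsistency is narrower: footnote g provides for a test at early termination, the Part B schedule has an EOB/ET column without one, and Part C is scheduled differently.

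**Conclusion.** The point holds as a mismatch between passages. The contraception period is 165 days after the last dose. The participant reporting duty is worded to stop with participation, which on nominal days is 45 to 59 days earlier in Part B. In Part C it is about 109 days earlier if follow-up ends at Week 14, or 81 days if the two follow-ups are consecutive. Pregnancies arising in that interval are not clearly required to be reported.

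In Part B no test is scheduled after Day 91, 21 days before the last dose, and the EOB/ET column is empty despite Table 1 footnote g.

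The Part B figures rest on dates in the tables and on the stated cap. The Part C figure is less certain, because it assumes a last dose at Week 6 and a Final Visit no later than Week 14. The conflicting maintenance durations and the undated Final Visit could each move it. The reporting wording needs correcting whichever Part C figure applies.

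**What to change.** 1. Reconcile Section 10.7 with Section 5.1 criterion 6 and Section 6.5.3.2, so that the reporting periods for participants and for partners both match the protocol's existing 165-day period. Apply one period throughout Section 10.7, and have sites tell participants at the last visit to notify them of a pregnancy within it.
2. Reconcile the EOB/ET column of Protocol Table 3 and SAP Table 3-3 with Table 1 footnote g and with the Part C schedule, so that the three agree on whether a test is done.
3. Date the Part C Final Visit, and reconcile the 81 days of maintenance in Section 3.4.2.3 with the approximately 6 weeks stated elsewhere, so that the end of the 165 days can be fixed.
4. Section 10.7 refers to Section 6.5.3 for pregnancy testing and the definition of childbearing potential. That section as shown contains neither, so correct the reference or supply the text.

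The cost is protocol and SAP wording and, if the tables are aligned with footnote g, a pregnancy test at a visit that already takes place and for which Table 3 already schedules urinalysis. No visits are added. The downside is an occasional pregnancy report after database lock.
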